## Abstract

object name	Application of PDCA Cycle in Tracheal Intubation Training for Emergency Medicine Residents
goal of study	
Tracheal intubation is a high-risk, time-sensitive procedure essential in emergency airway management. Junior emergency medicine (EM) residents often face challenges in mastering this critical skill. The Plan–Do–Check–Act (PDCA) cycle is a structured educational framework that may enhance procedural competency through iterative improvement. This study aimed to evaluate the impact of a PDCA-based training model on intubation performance among EM residents.

research design	
This was a prospective observational study conducted in the emergency department (ED) of a tertiary teaching hospital. A PDCA-based clinical skills training program was formally implemented in the department beginning in October 2024. Residents who performed tracheal intubation procedures from October 2023 to September 2023 were assigned to the control group, representing training prior to PDCA implementation. Those who performed intubations from October 2024 to September 2025 constituted the intervention group, following the adoption of the PDCA cycle teaching model.
 
Outcomes were compared between groups, including: success and failure rates of tracheal intubation, procedure completion time, incidence of airway-related local trauma or bleeding, reintubation within 3 days due to airway injury, and resident satisfaction with training.
 
The study protocol was approved by the institutional ethics committee. Written informed consent was obtained from all participants, and all procedures complied with the Declaration of Helsinki

	(2013).umulative hospitalization time and mortality were collected.
Total number of cases studied	100 cases

statistical method	All statistical analyses were performed using SPSS version 26.0 (IBM Corp., Armonk, NY, USA). Categorical variables, including intubation success rate, incidence of local airway trauma, extubation failure due to airway injury, and resident satisfaction rate, were expressed as counts and percentages [n (%)], and were compared between groups using the chi-square test ( $\chi^2$ test) or Fisher's exact test, as appropriate. Continuous variables, such as intubation completion time, were tested for normality using the Shapiro–Wilk test. Variables not conforming to a normal distribution were expressed as median (interquartile range) and compared using the Mann–Whitney U test. A two-tailed P value $< 0.05$ was considered statistically significant.

#### Exclusion Criteria

- Residents who refuse to participate or withdraw

	
informed consent.
 
 
Residents with prior advanced airway fellowship training or extensive intubation experience (>50 independent intubations).
 
Residents unable to complete the full PDCA-based training program due to absence, scheduling conflicts, or early rotation termination.
 
Residents with medical conditions or personal circumstances that could interfere with participation or data collection integrity.
 

Research period	October 2024 1 to September 30 2025

## —. Research background

Tracheal intubation is a cornerstone of emergency airway management, critical in conditions such as cardiac arrest, trauma, respiratory failure, and airway obstruction(1–3). Despite its lifesaving role, tracheal intubation remains one of the most technically challenging procedures for emergency medicine (EM) residents(4–6). Studies have consistently shown that junior residents face difficulty in achieving first-pass success, often resulting in repeated attempts, airway trauma, hypoxia, aspiration, and adverse patient outcomes(2,7–10). The steep learning curve, high cognitive load, and pressure inherent to emergency settings further exacerbate the risk of procedural failure(11–13).

Traditional didactic training often lacks the iterative reinforcement and feedback required for skill retention and real-time adaptation(14–15). In response, the Plan–Do–Check–Act (PDCA) cycle, originally introduced by Deming for industrial quality improvement, has been adopted in medical education to improve procedural competency(16–18). The PDCA framework promotes continuous evaluation and refinement of teaching strategies, aligning well with modern competency-based medical education paradigms(19–21).

Recent applications of PDCA in healthcare simulation and airway management training have demonstrated significant benefits, including improved first-pass success rates, reduced complication incidence, and enhanced learner satisfaction(22–29). Particularly in pediatric and neonatal intensive care units, PDCA-guided programs have standardized procedural education and bridged the gap between theory and practice(25–26). However, its integration into emergency airway training—a domain defined by unpredictability, urgency, and complexity—remains

underexplored(30–34).

## 二、 research objective

This study aims to evaluate the impact of a PDCA cycle-based tracheal intubation training model for EM residents. We hypothesize that such structured, iterative, and feedback-driven training can significantly enhance intubation success, procedural efficiency, safety, and trainee confidence in high-stakes emergency environments.

## 四、 case selection

### Inclusion Criteria:

- (1) Emergency medicine residents rotating in the emergency department during the study period.
- (2) Residents who are required to perform tracheal intubation as part of clinical training.
- (3) Residents who have completed baseline theoretical and simulation-based airway management training.

① Voluntary participation with written informed consent.

### Exclusion Criteria:

- (1) Residents who refuse to participate or withdraw consent.
- (2) Residents with prior advanced airway fellowship training or extensive intubation experience (>50 independent intubations).
- (3) Residents who are unable to complete the full PDCA-based training program due to absence or rotation schedule.
- (4) Any medical condition or circumstance deemed by investigators to interfere with participation or data integrity.

#### Exclusion Criteria

- Residents who refuse to participate or withdraw informed consent.
- Residents with prior advanced airway fellowship training or extensive intubation experience (>50 independent intubations).
- Residents unable to complete the full PDCA-based training program due to absence, scheduling conflicts, or early rotation termination.
- Residents with medical conditions or personal circumstances that could interfere with participation or data collection integrity.

#### 五、research method

This was a prospective observational study conducted in the emergency department (ED) of a tertiary teaching hospital. A PDCA-based clinical skills training program was formally implemented in the department beginning in January 2024. Residents who performed tracheal intubation procedures from January 2023 to December 2023 were assigned to the control group, representing training prior to PDCA implementation. Those who performed intubations from January 2024 to December 2024 constituted the intervention group, following the adoption of the PDCA cycle teaching model.

Outcomes were compared between groups, including: success and failure rates of tracheal intubation, procedure completion time, incidence of

airway-related local trauma or bleeding, reintubation within 3 days due to airway injury, and resident satisfaction with training.

The study protocol was approved by the institutional ethics committee. Written informed consent was obtained from all participants, and all procedures complied with the Declaration of Helsinki (2013).

### **Stage 1: Plan**

To enhance residents' competency in tracheal intubation, the emergency department developed a structured PDCA-based training protocol:

(1) Didactic Sessions: Weekly theoretical instruction was conducted by senior attending physicians in small-group settings every Wednesday afternoon. Topics included indications and contraindications of adult intubation, airway anatomy, identification of difficult airway, rapid sequence induction (RSI), and management of complications.

(2) Simulation Training: Every Thursday, high-fidelity airway mannequins were used for hands-on simulation of various clinical scenarios (e.g., COPD exacerbation, upper gastrointestinal bleeding, comatose patients). Instructors demonstrated procedures, emphasized key actions and safety checkpoints, and provided immediate corrective feedback during resident practice.

(3) Clinical Practice: Residents were allowed to perform intubations in clinical settings only after passing theoretical and simulation assessments. Based on experience level, instructors assigned appropriate cases. Stable patients with lower intubation difficulty were prioritized for beginners, with gradual progression to more complex scenarios.

### **Stage 3: Check**

The effectiveness of PDCA implementation was assessed through both process monitoring and outcome evaluation. Data collected from the intervention group were compared to baseline data from the control group.

Definitions:

Successful intubation: Independent completion of tracheal intubation by the resident following standard operating procedures.

Failed intubation: Three or more unsuccessful attempts to pass the endotracheal tube to appropriate depth.

Airway trauma: Presence of fresh blood in the airway post-intubation, excluding bleeding from preexisting pathology (e.g., subglottic mass, pulmonary hemorrhage).

Extubation failure due to airway injury: Need for reintubation within 72 hours despite meeting extubation criteria, confirmed by laryngoscopic evidence of edema, vocal cord paralysis, granulation, or subglottic stenosis.

Resident satisfaction: Evaluated via anonymous questionnaire covering

subjective learning experience and perceived value of training during their ED rotation.

#### **Stage 4: Act**

Based on outcome data and feedback, the following improvements were implemented in the subsequent PDCA cycle:

(1)Simulation Enhancement: Increased frequency of practice sessions for novice residents; established a “failed simulation bank” focused on difficult airway scenarios.

(2)Visualization Tools: Introduced video laryngoscopy into teaching to enhance visualization and facilitate real-time instruction.

(3)Assessment System: Developed a standardized scoring system for intubation performance using instructor ratings, video review, and checklist-based evaluation for closed-loop feedback.

In addition, procedural nursing aspects before and after intubation were emphasized, including:pre-procedure safety checklists,continuous monitoring of vital signs,reinforcement of sterile techniques,timely replacement of tube fixation materials,stabilization of head and body position to prevent tube displacement, and visible labeling of critical lines and tubes.

All such measures were progressively incorporated into the next iteration of PDCA-based training to ensure quality, consistency, and sustainability.

#### **六. Observation items and detection time points**

##### **1. First-Attempt Success Rate of Tracheal Intubation**

Observation item: Whether residents complete intubation successfully on the first attempt.

Detection time point: Immediately during the procedure, confirmed by chest

rise, end-tidal CO2, auscultation, or chest X-ray.

2. Intubation Completion Time

Observation item: Time required for residents to complete intubation.

Detection time point: Measured in seconds from insertion of the laryngoscope to confirmation of successful tube placement.

3. Incidence of Local Airway Trauma

Observation item: Presence of visible bleeding or mucosal injury during suctioning after intubation.

Detection time point: Within 24 hours post-intubation.

4. Extubation Failure Due to Airway Injury

Observation item: Need for reintubation caused by airway injury (edema, vocal cord paralysis, granulation, or subglottic stenosis).

Detection time point: Within 72 hours post-extubation.

5. Resident Satisfaction With Training

Observation item: Residents' subjective evaluation of the PDCA training program.

Detection time point: At the end of the emergency department rotation, via anonymous questionnaire.

七. standards for efficacy appraisal

1. Primary Efficacy Standard

First-attempt success rate of tracheal intubation is the primary indicator of efficacy.

An intervention is considered effective if the PDCA-trained group demonstrates a statistically significant improvement compared with the control group ( $P < 0.05$ ).

2. Secondary Efficacy Standards

Intubation completion time: A reduction in median time compared with controls indicates improved procedural efficiency.

Incidence of airway trauma and extubation failure: Lower rates suggest enhanced safety and procedural proficiency, even if not statistically significant.

Resident satisfaction score: Higher satisfaction rates reflect better training experience and improved confidence.

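### Completion time is undefined for failed intubations and has no single stop event, so the time comparison covers only successes and may mix end points between periods

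*Protocol*

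**What the plan says.** All references are to the Protocol.

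- **Section 六, item 2 (Intubation Completion Time).** The item observed is "Time required for residents to complete intubation". The clock is "Measured in seconds from insertion of the laryngoscope to confirmation of successful tube placement".
- **Section 六, item 1 (First-Attempt Success Rate).** This is the only place that says how placement is confirmed. It gives chest rise and end-tidal CO2, then "auscultation, or chest X-ray", as alternatives. Item 2 does not refer to this list and names no method.
- **Stage 3: Check, Definitions.** A failed intubation is "Three or more unsuccessful attempts to pass the endotracheal tube to appropriate depth". Success means that the resident completed the procedure independently.
- **Section 七.** "First-attempt success rate of tracheal intubation is the primary indicator of efficacy". For time, "A reduction in median time compared with controls indicates improved procedural efficiency"; this reading is not tied to a significant test.
- **Section 七, Comprehensive Appraisal.** The programme is judged efficacious on a significant primary result together with favourable secondary trends. Continuous outcomes are compared by Mann-Whitney U.

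Nowhere does the protocol give a value, ceiling or rank for a procedure that did not succeed.

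**The concern.** Two features of the definition affect what the comparison of times can mean.

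First, the clock has a stop event only when placement succeeds. A procedure the resident did not complete has no time to enter in the test. The groups are then compared among successes only, and success is the thing the training is expected to change. If difficult cases are both slower and more likely to fail, the group with more failures loses more of its slowest cases and looks faster than it was. If the training works, that is the control group, so a real gain in speed would be understated and could in some settings appear as a loss.

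Second, the confirming moment is not fixed. A bedside sign is available sooner than a film, and the outcome is recorded in seconds. The two groups come from different calendar periods, and nothing in the protocol holds the method of confirmation constant between them. A change in method would move the recorded time with no change in how fast residents intubate.

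At stake is a secondary outcome whose median is read directly as evidence of efficiency and counts towards the overall appraisal.

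**Working it through.** **No figure to reproduce.** The protocol states no failure rate, median, spread, target difference or power for completion time, and its total of 100 cases is not split by group. The definition is checked by reading; the sizes below are illustrations.

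**Reading.** Set side by side, the stop event in item 2 requires success, while the Stage 3 definition describes an outcome without it. The set of procedures with a time is therefore the set of successes. Item 2 leaves the confirming event open. Either the item 1 list is carried over, giving four possible stop points, or it is not, and the stop point is unspecified. It is not uniform on either reading.

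**Illustration A: successes only, no true difference in speed.** Assumed: 50 per group (half of 100), log-normal times with median 60 s and log-SD 0.5, Mann-Whitney two-sided at 0.05. Failure depends on case difficulty (the standardised log time) through a logistic slope varied from 0 (unrelated) to 4 (strong), with the intercept set to give the stated failure rate.

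| Failure, control v PDCA | PDCA significantly slower |
|---|---|
| 30% v 10% | 2% to 29% |
| 10% v 5% | 2% to 5% |

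The nominal rate in one direction is 2.5%. At slope 0 there is no bias; the upper ends need a strong link. At the strong end with 30% v 10%, the success-only medians are about 57 s for PDCA and 50 s for control, a gap of 57 − 50 = 7 s where none exists. With 2,000 runs the simulation error on 29% is √(0.29 × 0.71 / 2000) ≈ 1 percentage point.

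**Illustration B: a different failure model, with a true difference.** Assumed: log-SD 0.6, and a procedure fails if its latent time exceeds 180 s. For failure rate f, the log-mean is m = ln 180 − 0.6 × z(1 − f). The median of all procedures is exp(m), and the median of successes is exp(m + 0.6 × z((1 − f)/2)).

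- f = 20%: m = 5.193 − 0.6 × 0.842 = 4.688. All: 109 s. Successes: exp(4.688 − 0.6 × 0.253) = 93 s.
- f = 10%: m = 5.193 − 0.6 × 1.282 = 4.424. All: 83 s. Successes: exp(4.424 − 0.6 × 0.126) = 77 s.

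The difference in medians is 25 s among all procedures (before rounding) and 93 − 77 = 16 s among successes. With 10% v 5% it falls only from 16 s to 13 s. In this model the difference shrinks but does not reverse.

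**Illustration C: mixed stop points, no true difference.** Times as in A; X-ray confirmation is assumed to add 600 s.

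| X-ray share, control v PDCA | PDCA falsely significantly faster |
|---|---|
| 10% v 10% | 2.7% (nominal 2.5%) |
| 20% v 10% | about 12% |
| 30% v 10% | about 41% |

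Section 七 reads the median, not the test. At 30% v 10%, with 10 s assumed for bedside confirmation, the control median exceeds the PDCA median by 18.3 s on average. If PDCA had the larger X-ray share, the error would run the other way.

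**The case against.** **The X-ray stop is an inference.** A reader might infer that the protocol stops the clock at a chest X-ray. It does not say so. The list belongs to item 1, where detection is placed at the time of the procedure, and a film sits poorly with that and with a time in seconds. This stands: the supportable statement is that item 2 names no event and the only list available is not a single event. Bias from this source also requires the mix of methods to differ between periods, and nothing in the protocol shows that it did.

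**Success-only analysis is not instructed.** A reader might infer that the plan orders failures to be dropped. It does not, and rules for cases without a value are often left to an SAP, which is not shown here. This stands in part. The protocol itself fixes the stop event, and that definition is what leaves failures without a time, so the correction belongs there.

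**The excluded group may be small.** Failure needs three or more unsuccessful attempts, so a success on the second or third attempt still has a time. This stands, and is why the lower failure rates are shown.

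**Ranking failures worst does not measure speed.** A reader might take the higher rejection rate of such an analysis as power recovered for speed. It is not. With 30% v 10% failure and no difference in speed, that analysis favours PDCA in 11% to 45% of trials, because it also detects the difference in failures. This stands and governs how the result must be labelled.

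**Time cannot decide the trial alone.** The overall appraisal also needs a significant primary result and several favourable secondary trends. This stands.

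**Conclusion.** The concern holds for a secondary outcome and should be corrected. As defined, completion time exists only for successful procedures, and its stop point is not one named event. The first follows directly from the wording of item 2; the second comes from item 2's silence read with the list in item 1.

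The size cannot be derived from the protocol. Under the assumptions shown, conditioning on success ranges from negligible (failure 10% v 5%, or failure unrelated to difficulty) to serious (29% false findings of slower performance at 30% v 10% with a strong link). Mixed stop points do no harm when shares are equal and substantial harm when they are not. The two effects can run in opposite directions, so the sign of the net error is unknown.

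The documents do not support the stronger conclusions that the time result will be reversed, that confirmation practice changed between periods, or that this outcome alone could produce a false claim of efficacy.

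**What to change.** 1. **Stop event.** In section 六, item 2, end the clock at one named bedside event recorded in both periods, and not at chest X-ray. This concerns the measurement only, not how placement is confirmed in care. First check that the control-period records hold that event; the protocol does not show that they do. If they do not, state that the stop event varies and treat the time result as descriptive.
2. **Failed procedures.** Compare all intubations by Mann-Whitney, giving the worst rank to procedures that failed or were taken over by another operator. Label this a combined comparison of time and failure, not of speed alone.
3. **Description.** Report times among successes beside it, with the number of procedures excluded in each group.

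The cost is a change to one definition and one analysis rule, plus a check of the control-period records. The drawback is that the ranked comparison partly repeats the success outcome, so it should not be counted in the overall appraisal as independent evidence of efficiency.

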### 3. Comprehensive Appraisal

The PDCA training program will be deemed efficacious if it results in significant improvement in the primary outcome and favorable trends across multiple secondary outcomes.

Statistical analyses will use chi-square tests for categorical variables and Mann-Whitney U test for continuous variables, with  $P < 0.05$  considered statistically significant.

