### 十. Statistical processing

All statistical analyses were performed using SPSS version 26.0 (IBM Corp., Armonk, NY, USA). Categorical variables, including intubation success rate,

incidence of local airway trauma, extubation failure due to airway injury, and resident satisfaction rate, were expressed as counts and percentages [n (%)], and were compared between groups using the chi-square test ( $\chi^2$  test) or Fisher's exact test, as appropriate. Continuous variables, such as intubation completion time, were tested for normality using the Shapiro–Wilk test. Variables not conforming to a normal distribution were expressed as median (interquartile range) and compared using the Mann–Whitney U test. A two-tailed P value  $< 0.05$  was considered statistically significant.

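### The efficiency conclusion in section 七.2 rests on the direction of the medians alone and is not tied to the test the protocol plans for completion time

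*Protocol*

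**What the plan says.** The Protocol deals with completion time in four places.

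- **Objective (section 二).** Efficiency is one of four effects hypothesised for the training, which "can significantly enhance intubation success, procedural efficiency, safety, and trainee confidence in high-stakes emergency environments".
- **Secondary Efficacy Standards (section 七.2).** "Intubation completion time: A reduction in median time compared with controls indicates improved procedural efficiency". The next item, on airway trauma and extubation failure, reads: "Lower rates suggest enhanced safety and procedural proficiency, even if not statistically significant".
- **Comprehensive Appraisal (section 七.3).** The planned analysis is the "Mann-Whitney U test for continuous variables, with $P < 0.05$ considered statistically significant". The programme is judged efficacious if the primary outcome improves significantly and several secondary outcomes trend favourably.
- **Statistical processing (section 十, repeated in the Abstract).** "Continuous variables, such as intubation completion time, were tested for normality using the Shapiro–Wilk test". Then: "Variables not conforming to a normal distribution were expressed as median (interquartile range) and compared using the Mann–Whitney U test". The criterion is two-sided: "A two-tailed P value $< 0.05$ was considered statistically significant".

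The primary standard in section 七.1, by contrast, is met only by a statistically significant improvement at P < 0.05.

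**The concern.** Section 七 sets the standards by which results are appraised, so its sentences will be used to decide what may be claimed. For completion time, the only input named is whether the PDCA median is below the control median. A one-second difference would satisfy that. The protocol plans a test of the same endpoint but does not say that the conclusion depends on its result.

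What is at stake is the secondary claim on efficiency. With a non-significant test, or even with a truly slower PDCA group whose sample median happens to fall lower, the wording still allows a report that efficiency improved. The same result could also be counted as one of the favourable trends in 七.3.

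**Working it through.** The protocol gives no power, error rate or sample-size derivation for completion time, so there is no figure of its own to reproduce. The check compares how often the efficiency statement would be made under the two readings of 七.2.

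**Inputs from the Protocol.** Total of 100 cases (Abstract), time measured in seconds (section 六), two-sided alpha 0.05, Mann-Whitney U (section 七.3).

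**Assumptions, as the Protocol does not give these.** The 100 cases are intubations, split 50/50, 40/60, 30/70 or 70/30. Times are log-normal with median 45 s and log-SD 0.3, 0.5 or 0.8. The distribution is the same in both periods. Each scenario used 10,000 simulated trials.

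**Step 1. Literal reading: conclude if median(PDCA) < median(control).** With equal groups, continuous times and no effect, the groups are exchangeable and the probability is 0.5 by symmetry, whatever the distribution. Simulated values over all splits and log-SDs:

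- continuous times: 0.49 to 0.51
- times rounded to whole seconds: 0.47 to 0.50 (tied medians in 2% to 6% of trials)

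**Step 2. Tested reading: the same direction and two-sided Mann-Whitney P < 0.05.** The nominal rate is 0.05 / 2 = 0.025. Simulated values were 0.021 to 0.027.

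**Step 3. Clustering within residents.** With 10 residents per group, five intubations each, an assumed ICC of 0.2 and log-SD 0.5, the literal rule stays at 0.50. The tested rule rises to 0.073, because Mann-Whitney treats the intubations as independent.

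**Step 4. If PDCA truly lengthened times.** With 50 per group, the standard error of the difference in log medians is about 1.253 × SD × √(2/50) = 1.253 × SD × 0.2. The literal rule then fires with probability Φ(−ln(ratio) / SE), where ln(1.05) = 0.0488 and ln(1.10) = 0.0953.

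| Log-SD | SE | True 5% slowing | True 10% slowing |
|---|---|---|---|
| 0.3 | 0.075 | Φ(−0.65) = 0.26 | Φ(−1.27) = 0.10 |
| 0.5 | 0.125 | Φ(−0.39) = 0.35 | Φ(−0.76) = 0.22 |
| 0.8 | 0.200 | Φ(−0.24) = 0.40 | Φ(−0.48) = 0.32 |

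Unlike the 50%, these figures depend on the assumed spread.

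**Step 5. Which reading does the text fix?** Significance is required for the primary outcome in 七.1 and 七.3. It is expressly waived for trauma and extubation failure in 七.2. For completion time it is neither required nor waived, and 七.3 then asks only for trends on secondaries. The text therefore allows both readings, with rates of about 50% and about 2.5%.

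**The case against.** The strongest reply is that the endpoint does have a test. Section 十 and the Abstract name completion time as a continuous variable and set a two-tailed 0.05 criterion, and 七.3 repeats Mann-Whitney at P < 0.05 in the same section as the disputed sentence. The explicit waiver covers only trauma and extubation failure and would be redundant if every item in 七.2 already ignored significance. Mention of the median also points to the non-normal branch of section 十, which is the one tested by Mann-Whitney. On this view the sentence merely explains what a shorter time means.

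Much of this stands. A reader might infer that the protocol has no test for completion time; that is not so. The gap is a missing link between test and conclusion. The tested reading is also a fair one. It is not secured, however: 七.3 itself separates significance for the primary from mere direction for the secondaries, the satisfaction item in 七.2 is also purely directional, and a lower median is not the quantity that Mann-Whitney tests.

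Two smaller points also stand. Section 十 plans Mann-Whitney only for variables that fail the normality check, whereas 七.3 plans it without that condition. And the 2.5% cannot be promised if intubations cluster within residents.

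**Conclusion.** The point holds as a defect of wording in a stated criterion. Section 七.2 lets a non-significant reduction in median time be reported as improved efficiency. Under the literal reading this happens about 50% of the time when training has no effect. Tied to the planned test in the favourable direction, it falls to about 2.5% with independent intubations, or about 7% at five intubations per resident and ICC 0.2.

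Both figures assume no secular or case-mix difference between the control and PDCA periods, which a before-after comparison does not ensure. The split, the time distribution and the ICC are assumptions.

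A reader might infer that an ineffective programme would be declared efficacious half the time. The protocol does not support that: the overall verdict in 七.3 also requires a significant primary outcome. The 50% applies to the secondary efficiency statement alone. The change should be made, but it does not threaten the main conclusion of the study.

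**What to change.** Replace the completion-time sentence in section 七.2 with wording such as: *Improved procedural efficiency is concluded only if completion time is shorter in the PDCA group and the planned two-tailed Mann-Whitney U test gives P < 0.05. The Hodges-Lehmann difference is reported with its 95% confidence interval. Otherwise the difference is reported descriptively, as not demonstrated.*

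This uses the test as stated in 七.3. Section 十 should be aligned with it, so that the test behind the conclusion does not depend on a normality check in one place and not in the other.

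The cost is one reworded sentence and that alignment; no new data are needed. The downside is that the efficiency claim becomes harder to make.
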